1 INTRODUCTION

1.1 Purpose of Statistical Analysis Plan

This document states in detail the plans for the analysis of the main outcome of the study and of the quantitative data that will be collected in the Nkateko trial. The quantitative outcome data will be reported in one or more principal papers on the results of the trial. Subsequent papers, which will be more exploratory or descriptive, will not be bound by this strategy and will be clearly identified as such.

1.3 Summary

South Africa has a high and rising prevalence of hypertension, many people are unaware they have the condition and pharmaceutical management is often inadequate. Until recently, primary care clinics focused on management of acute conditions, but recent government initiatives are shifting the focus to management of chronic disease, including HIV and hypertension. This cluster-randomised controlled trial will test the effectiveness of a new clinic-based lay health worker to supplement government initiatives and support care of chronic disease.

1.4 Changes from planned analysis in the protocol

No changes are planned from the analysis described in the protocol.

2 STUDY OBJECTIVES AND ENDPOINTS

2.1 Study Objectives

2.1.1 Primary Objective

To compare the effectiveness of a quality improvement intervention involving use of clinic based lay health workers to 'usual care', in improving access to care, adherence to treatment, and management of hypertensive patients, in rural South Africa

2.2 Outcome Measures

2.2.1 Primary Outcome

A population level measure of hypertension control will be derived from cross-sectional surveys carried out before and after the intervention. This primary outcome will be the change between the two surveys in the percentage of people in the population who have elevated blood pressure that is combined with other factors resulting in a risk profile that indicates moderate or greater added risk of cardiovascular disease. More detailed definitions of outcomes are described in section 5.7.

2.2.2 Secondary Outcomes

- a) Change in proportion of the population with undiagnosed hypertension (see table 10 in the appendix)
- b) Change in the proportion of the population reporting they had had their blood pressure measured (see table 10 in the appendix),
- c) Change in the proportion of the population reporting that they are using medication for hypertension (see table 10 in the appendix)
- d) Change in the proportion of the population at different levels of blood-pressurerelated cardiovascular risk by age group and sex (see tables 5, 6, 7, 8 and 9 in the appendix)
- e) Change in the proportion of people in the population reporting that they have attended a clinic in the last year (see table 10 in the appendix)
- f) Retention in care of people with diagnosed hypertension defined by the proportion of appointments kept during the study period (see table 11 in the appendix)

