3 STUDY METHODS

3.1 Overall Study Design and Plan

We will conduct a cluster-randomised trial in tandem with a detailed realist evaluation. drawing on global experience of evaluating complex interventions^{1,2}. The units of randomisation will be health facilities and their surrounding catchment populations. We propose to randomise eight clinics, four of which will receive the intervention. To achieve our primary outcome, we aim to both increase the proportion of the population under active management for their hypertension and reduce the level of blood pressure in those patients already receiving care. For this reason, the outcome of the trial will be measured at population level, and we estimate that the trial has a power of above 80% to detect an 11% to 13% reduction in the proportion of the population at moderate or greater cardiovascular risk as a result of their blood pressure and other risk factors. Realist evaluation will provide data on adaption of the intervention to the context, individual and organizational processes of change as well as contextual factors that influence outcomes³. We are collecting data at two cross-sectional points 24 months apart: baseline (when intervention is introduced) and at the end of intervention at each clinic to provide data on the sustainability of the intervention. The detailed study methods are described in the following sections.

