4.2 Follow up

The follow-up survey will use a different sample, which will be selected using the same age/sex distribution. The data collection will be the same as that listed above for the baseline survey.

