6 ANALYSIS OF PRIMARY OUTCOME

6.1 Definition of outcome measure

The primary outcome will be the change in the percentage of people in the population who have elevated blood pressure that is combined with other factors resulting in a risk profile that indicates moderate or greater added risk of cardiovascular disease. as indicated by the shaded cells in Table 2. This includes individuals with either: a systolic blood pressure of 160 and above, diastolic of 100 and above, systolic blood pressure of 140-159 plus one or more risk factors, or diastolic blood pressure 90-99 plus one or more risk factors. These data will be obtained from two population surveys (one before the start of the trial and one after the trial ends).

Table 2. Modified South African Guideline: Stratification of cardiovascular risk in patients with hypertension (defined as SBP>139 or DBP>89)

Blood pressure (mmHg)	Presence of risk factors or other conditions						
	No risk factors	One or two risk factors	Three or more risk factors or diabetes	Associated clinical conditions			
SBP 140 -159 or DBP 90-99	Low Added Risk	Moderate Added Risk	High Added Risk	Very High Added Risk			
SBP 160 -179 or DBP 100-109	Moderate Added Risk	Moderate Added Risk	High Added Risk	Very High Added Risk			
SBP 180 + or DBP 110+	High Added Risk	Very High Added Risk	Very High Added Risk	Very High Added Risk			

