6.3 Primary analysis

The analysis of the primary outcome (binary, as defined above) will be done in three steps Thus, firstly, a group level analysis of the overall effect of the intervention using the test of differences in two proportions (within each group at baseline and after follow-up and between intervention and control clusters) will be conducted adjusting for the design effect and clustering correction factors for each group. We will not use the usual Pearson's Chi-Square test which assumes independence as our data are clustered. Intra-class correlation (ICC) adjusted Pearson's Chi-square versions will be used as those used by Reed. These will involve creating and pilot testing a STATA program to perform these adjusted Chi-Square based analyses for binary outcome data¹⁰⁻¹².

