6.5 Other analysis supporting the primary analysis (including sensitivity analyses)

Apart from looking at the observed effect of the intervention, a sensitivity analysis will be conducted:

- 1. The primary analysis on hypertensive drugs described in section 5.7 excludes from the analysis those who do not name any specific drugs we will include these in a sensitivity analysis.
- 2. We will undertake sensitivity with individuals analyzed in the "last" clinic that they attended.
- 3. We will adjust for potential confounding factors using the two stage regression model¹³. Firstly, two logistic regression models for control and intervention clinics that include covariates will be fitted separately, with individual level covariates such as gender and age. Secondly, based on residuals from the first stage we will aggregate outcomes to cluster level and cluster/clinic level factors (e.g. clinic size) will be used in regression modeling at the cluster level to test the effect of the intervention.
- 4. In order to compare the results from the two stage regression an alternative procedure will be used, the mixed effects model adjusting for covariates.

Model sensitivity to the individual-level data will be assessed on different temporal covariance structures (exchangeable, auto covariance and unstructured) on the final model. Such assessment will be made possible because of the many appointments with the 21 months of follow-up.

Thus, endeavors to ensure data are complete will be explored rigorously taking advantage of this longitudinal nature of data and, in the process a report for missing data

by variable will be compiled. This will help to classify the missing data as either missing at random (MAR) or missing not at random (MNAR). Assuming the data are MAR the proposed mixed logistic models should sufficiently handle these. If otherwise, as with MNAR we will employ data imputation procedures accordingly, taking caution not to distort the patterns observed from the data. However, as this is an area in which research is ongoing, this will be an exploratory analysis, not reported in the main trial report, and drawing on latest research. The dummy tables for these and details on how imputation on clustered data will be done, will not be provided in this analysis plan.

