Blood pressure (mmHg)	Presence of risk factors or other conditions							
No risk of hypertension	No risk factors	One or two risk factors	Three or more risk factors or diabetes	Associated clinical conditions				
SBP 140 -159 or DBP 90-99	Low Added Risk	Moderate Added Risk	High Added Risk	Very High Added Risk				
SBP 160 -179 or DBP 100-109	Moderate Added Risk	Moderate Added Risk	High Added Risk	Very High Added Risk				
SBP 180 + or DBP 110+	High Added Risk	Very High Added Risk	Very High Added Risk	Very High Added Risk				

Use Table 4 to allocate individuals to level of risk, which is then used to complete Table 3

Blood pressure (mmHg)	Presence of risk factors or other conditions							
No risk of hypertension	No risk factors	One or two risk factors	Three or more risk factors or diabetes	Associated clinical conditions				
SBP 140 -159 or DBP 90-99								
SBP 160 -179 or DBP 100-109								
SBP 180 + or DBP 110+								

Table 5: Proportion of people with risk factors in the control clinics at baseline

Nkateko Analysis Plan 6th April 2016 final

Blood pressure (mmHg)	Presence of risk factors or other conditions							
No risk of hypertension	No risk factors	One or two risk factors	Three or more risk factors or diabetes	Associated clinical conditions				
SBP 140 -159 or DBP 90-99								
SBP 160 -179 or DBP 100-109								
SBP 180 + or DBP 110+								

Table 6: Proportion of	people with risk factors	in the control clinics	at end of intervention

Table 7: Proportion of	neonle with ris	k factors in the	intervention	clinics at baseline

Blood pressure (mmHg)	Presence of risk factors or other conditions								
No risk of hypertension	No risk factors	One or two risk factors	Three or more risk factors or diabetes	Associated clinical conditions					
SBP 140 -159 or DBP 90-99									
SBP 160 -179 or DBP 100-109									
SBP 180 + or DBP 110+									

Blood pressure (mmHg)	Presence of risk factors or other conditions									
No risk of hypertension	No risk factors	One or two risk factors	Three or more risk factors or diabetes	Associated clinical conditions						
SBP 140 -159 or DBP 90-99										
SBP 160 -179 or DBP 100-109										
SBP 180 + or DBP 110+										

Table 8: Proportion of people with risk factors in the intervention clinics at end of intervention

Table 9: Change in level of cardiovascular risk of study population (primary and secondary outcomes)

Level of	Control			Interventio	n		Statistical Test
	· ·						

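### Cheap improvement: the primary outcome is framed as an unadjusted change between surveys, and no analysis adjusts for each clinic's baseline prevalence

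*SAP*

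**What the plan says.** Section 2.2.1 defines the outcome by subtraction: "This primary outcome will be the change between the two surveys". Section 6.1 repeats it: "The primary outcome will be the change in the percentage of people in the population". The Table 9 shell in Appendix B has columns for the change within each arm and ends in a test of the difference between those changes.

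The analysis text is less definite. Section 6.3 announces three steps but describes one, "a group level analysis of the overall effect of the intervention using the test of differences in two proportions", using clustering-adjusted chi-square tests within groups over time and between arms. It gives no formula for comparing the two changes.

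Baseline prevalence is not named as a covariate anywhere. In the supporting analyses of section 6.5, the individual covariates given are age and gender, and at the second stage "cluster/clinic level factors (e.g. clinic size) will be used in regression modeling at the cluster level".

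On design, section 3.1 says "We propose to randomise eight clinics, four of which will receive the intervention", and section 4.2 says "The follow-up survey will use a different sample". Section 3.5 assumes that the CV is similar in the two arms. Its Table 1 gives power for end-of-trial prevalences only.

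**The concern.** With four clinics per arm, precision is the main limit on what the trial can show. Subtracting the baseline gives it a fixed weight of one. That carries the baseline survey's sampling error and between-clinic variation into the result, and it pays off only if clinics keep much the same level over two years. Regressing follow-up prevalence on arm and clinic baseline targets the same randomised effect and lets the data set the weight.

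Table 1 also does not describe the power of the outcome as defined. It contains neither the extra variance of a change nor any correlation between surveys.

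**Working it through.** **Inputs from the SAP.** Eight clinics, four per arm (3.1). CV 0.132 and background prevalence 36% (3.5). An 11-point reduction is the effect for which power above 80% is claimed (3.5), taken here as 36% v 25%. Baseline respondents 3905 (5.11), so 3905/8 = 488 per clinic.

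**Assumptions.** Two-sided 5% level, equal clinic sizes, and the correlation of true clinic prevalence between surveys. The SAP gives none for the correlation, so it is ranged from 0 to 1.

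**Step 1: reproduce Table 1.** For a clinic-level t test with 6 degrees of freedom on follow-up prevalence alone, take V = p0(1−p0)/m + p1(1−p1)/m + CV²(p0² + p1²) and noncentrality d/√(V/4). With m = 500 this gives 97.9% for 36 v 21 (SAP 97.4%), 88.6% for 32 v 21 (SAP 87.7%) and 87.6% for 36 v 24 (SAP 85.4%). With m = 400 all twelve cells agree within 1.6 points. Table 1 is therefore consistent with a follow-up-only comparison.

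**Step 2: what subtraction adds at zero correlation.** For 36 v 25 with m = 488:
- Follow-up only: V = 0.000472 + 0.000384 + 0.017424 × (0.1296 + 0.0625) = 0.00420. Noncentrality = 0.11/√(0.00420/4) = 3.39.
- Two independent baseline clinic terms add 2 × (0.000472 + 0.017424 × 0.1296) = 0.00546, so V = 0.00966. Noncentrality = 0.11/√(0.00966/4) = 2.24.

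**Step 3: simulation.** 40,000 replicates per setting, with binomial clinic counts around normally distributed clinic levels. Raw change is tested on arm with 6 degrees of freedom. The adjusted analysis regresses follow-up on arm and clinic baseline with 5 degrees of freedom. Chance baseline imbalance and the cost of estimating a slope from eight points are therefore included. Two SD structures were run: SD proportional to prevalence, which the SAP's similar-CV assumption implies, and the same absolute SD (0.132 × 36%) throughout.

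| True correlation | Proportional SD: change v adjusted | Equal SD: change v adjusted |
|---|---|---|
| 0 | 47% v 70% | 43% v 60% |
| 0.5 | 67% v 77% | 64% v 68% |
| 0.7 | 80% v 84% | 78% v 77% |
| 0.9 | 93% v 93% | 94% v 90% |
| 1.0 | 98% v 97% | 99% v 96% |

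Type I error is about 5% for both methods.

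**Step 4: where adjustment costs most.**
- For 36 v 31, change is ahead at correlation 1.0 by about 2 points with proportional SD (48.8% v 46.4%) and by about 5 to 6 points with equal SDs.
- At correlation 0 with proportional SD, a follow-up-only comparison has 81% power and the adjusted analysis 70%. Estimating an uninformative slope costs about 10 points.

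**Step 5: equivalence.** Regressing change on arm and baseline gives the same arm estimate and standard error as regressing follow-up on arm and baseline. Only the baseline coefficient shifts, by one. The outcome can stay defined as change.

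**The case against.** The strongest reply is that this is a trade-off, not a free gain. Change v adjustment with eight clinics depends on a correlation and an SD structure that nobody has stated. The same catchments are surveyed with the same age and sex distribution, so clinic levels may well be stable. A different sample at follow-up adds sampling error, which the simulation already counts, and is not evidence of instability. In the range 0.7 to 1.0 the two methods differ by only a few points, and with equal SDs change is ahead. All of this stands.

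Three stronger readings are tempting, and the documents do not support them:
- A reader might infer that adjustment costs at most about a point. That holds for an 11-point effect with SD proportional to prevalence. It fails for equal SDs or smaller effects, and the small-sample cost of the slope is real.
- A reader might take the worst-case loss as the expected loss. It needs a correlation of zero, and the SAP gives no value.
- A reader might infer that the plan fixes a change-score test. It does not: 6.3 leaves the comparison of changes open, and the cluster-level regression in 6.5 could take baseline prevalence as a factor, although it does not name it.

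Nor is raw change invalid, since its type I error is correct.

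**Conclusion.** The point holds as a cheap improvement. The outcome definition and Table 9 use baseline prevalence only by subtraction, 6.3 leaves the comparison unspecified, and no analysis names baseline prevalence as a covariate.

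At 36% v 25%, baseline adjustment protects against a worst-case loss of about 17 points (equal SDs) to 23 points (proportional SD) if clinic levels are unrelated between surveys. It is close to neutral near a true correlation of 0.7. If clinics are highly stable it costs about 1 to 4 points, or up to about 6 for a 5-point effect. With the correlation unknown, that asymmetry favours adjustment. It is not the best analysis everywhere: with no correlation, follow-up alone does better.

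These figures rest on the assumed 5% two-sided level, equal clinic sizes, the SAP's CV and clinic-level t tests. They do not describe the chi-square procedure in 6.3, which cannot be simulated for change because it is not specified.

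**What to change.** In 6.3, specify the between-arm comparison as a clinic-level linear regression of follow-up prevalence (equivalently, of change) on arm and the clinic's baseline prevalence: eight points, with a t test and 95% CI on 5 degrees of freedom. Keep the simple difference in change in Table 9 as a secondary presentation, and align that table's test column with 6.3. In 3.5, report power for this analysis over a range of between-survey correlations, for both proportional and equal SDs. If the change score is preferred, state its test and justify the stability that it relies on.

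No new data are needed. The cost is one degree of freedom and about 1 to 6 points of power if clinic levels are highly correlated. The follow-up survey ended in November 2015 and the plan is dated April 2016, so the choice should be recorded before clinic identities are unblinded. Section 1.4 should be updated if the choice departs from the protocol.

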3 STUDY METHODS

3.1 Overall Study Design and Plan

We will conduct a cluster-randomised trial in tandem with a detailed realist evaluation. drawing on global experience of evaluating complex interventions^{1,2}. The units of randomisation will be health facilities and their surrounding catchment populations. We propose to randomise eight clinics, four of which will receive the intervention. To achieve our primary outcome, we aim to both increase the proportion of the population under active management for their hypertension and reduce the level of blood pressure in those patients already receiving care. For this reason, the outcome of the trial will be measured at population level, and we estimate that the trial has a power of above 80% to detect an 11% to 13% reduction in the proportion of the population at moderate or greater cardiovascular risk as a result of their blood pressure and other risk factors. Realist evaluation will provide data on adaption of the intervention to the context, individual and organizational processes of change as well as contextual factors that influence outcomes³. We are collecting data at two cross-sectional points 24 months apart: baseline (when intervention is introduced) and at the end of intervention at each clinic to provide data on the sustainability of the intervention. The detailed study methods are described in the following sections.

3.2 Study Population

The trial will be based in the Agincourt sub-district of Mpumalanga Province, South Africa. Since 1992 the MRC/Wits Rural Public Health and Health Transitions Research Unit (Agincourt) has collected population data, with vital events (pregnancy outcome, death, migration) updated yearly. The total population under surveillance is about 90,000 people (52,592 older than 18 years) who live in 15,500 households in 26 villages within a rural, former Bantustan area, with high labour migration.

Inclusion criteria for clusters (clinics): publically funded primary care clinics serving a population which includes people living in the Agincourt HDSS area.

Inclusion criteria for individuals participating in the cross-sectional surveys: Adults (male and female) aged over 18 years, and permanently resident in the Agincourt HDSS area. The sample was selected proportional to the full Agincourt population with oversampling on the older population.

Exclusion criteria for individuals participating in the cross-sectional surveys and the process evaluation interviews: women who report that they are pregnant, individuals who are unable to give informed consent or are unable to respond to the questionnaire.

3.3 Method of Randomisation

Randomisation took place in the community at a meeting of clinic staff and members of local clinic committees. Eight primary health care facilities were randomised. After showing sheets of paper with the names of the clinics to the meeting, they were put into sealed envelopes, several community members were invited to shuffle the envelopes, which were then put into a bag and seven other community members each in turn chose one envelope, and the chosen clinic was allocated to a slot in the order of intervention clinic, control clinic, intervention clinic, etc. Appendix A gives the summary notes for the randomisation meeting that was held.

3.4 Treatment masking (Blinding)

This is a trial of a health service intervention where blinding of participants was not possible. In addition, the field workers who collected the baseline and outcome measures live in the area and use the clinics, so they may be aware of which clinics had extra lay health workers. We will be recruiting and training the field team for the survey that will provide the outcome measure towards the end of the intervention. We will ensure that the field workers are told only that this is a survey on hypertension and clinic use. The hypothesis of the trial will not be disclosed. The statistician responsible for the main analysis will remain blinded to which clusters are intervention and non-intervention as far as possible.

3.5 Sample size determination

The two cross-sectional surveys, which will be used to assess the effectiveness of the intervention, will each include at least 4000 participants, giving approximately 500

people in each cluster. We adopted the use of the coefficient of variation (standard deviation of the cluster means divided by the overall mean) as used in similar study settings when we cannot get a good intra-cluster variation⁴⁻⁶. For a background prevalence of 36% (i.e. proportion of patients at moderate or greater risk of cardiovascular disease) and a coefficient of variation of 0.132 (error margin 4.5% (0.132 ± 0.045)) based on data collected in the same site in 2010, different scenarios of proportions of moderate or greater risk patients at the end of trial in the control and intervention arms and their associated power are shown in Table 1. Based on the scenario of a 15% difference (i.e. 36% in control vs 21% in intervention), the highest power will be 97.4% and we will have power of above 80% to detect an 11% absolute reduction of people at moderate or greater cardiovascular risk. These calculations assume that the coefficient of variation will be similar in the two groups and that effects of the interventions are similar across clusters.

	Control	"36%" No change	
	CV	0.132	
Intervention	"5% difference" 31%	20.7	
	"10% difference" 26%	68.6	
	"12% difference" 24%	85.4	
	"15% difference" 21%	97.4	
	Control	"34%" 2% change	
	CV	0.132	
Intervention	"3% difference" 31%	10.5	
	"8% difference" 26%	52.7	
	"10% difference" 24%	75.4	
	"13% difference" 21%	94.2	
	Control	"32%" 4% change	
	CV	0.132	
Intervention	"1% difference" 31%	4.3	
	"6% difference" 26%	35.2	
	"8% difference" 24%	58.4	
	"11% difference" 21%	87.7	

Table 1: Power	matrix of different scenari	ios
-----------------------	-----------------------------	-----

